## 9.5 Interim analysis

Does not apply to this study.

## **10. ETHICAL CONSIDERATIONS**

## **10.1 Regulation statement**

This study will be performed in accordance to the principles of the declaration of Helsinki as written by the WMO in 2013 (version 64) and according to the WMO.

## 10.2 Recruitment and consent

- ET patients that are registered at the hospital will be informed about the study. The principal investigator, and other neurologists within the hospital, will identify ET patients that might be suitable for the study, such as patients who visited the hospital for consultation. The treating physician can call the patient to inform them about the study if he/she thinks that this patient is suitable. Additionally, CTcue will be used to screen patients who otherwise would have been overlooked.
- A brochure will be used to recruit additional eligible patients outside of the hospital. This brochure will be shared via (social) media and via affiliated neurologists from other Dutch hospitals. ET patients screened through this screening method can themselves contact the investigator(s) directly for more information, without any referral from their physician. To filter out requests, the investigator will ask a few elementary questions from the inclusion criteria (e.g.: "Are you diagnosed with ET") to validate if patients should receive a formal patient information form (PIF). The investigator will consequently send the selected patients the PIF with an application form by mail. The PIF also contains a cover letter that explains why patients received this invitation.
- If a patient is willing to participate, he/she fills out the application form and sends it back. Patients are requested to return the forms within two weeks.
- Patients who did not return the form within two weeks, will be contacted with a reminder letter.
- If additional questions arise, patients can always contact the investigators or the independent physician.
- Patients who fulfil all the inclusion criteria will be contacted by the investigator, to schedule an appointment for the inclusion test. This will be done with a phone conversation, during which patients can ask additional questions.
- Patients that are not eligible will receive a phone call that they will not be able to participate. The investigator is then also able to answer additional questions.
- The patient and investigator will sign the informed consent at the start of the appointment in the hospital. If, due to the severity of the tremor, the patient is unable to sign the informed consent, a representative person will sign it for them. The informed consent covers both the inclusion tests as the intervention with the orthoses (see Section 7.3.1).

## 10.3 Objection by minors or incapacitated subjects

Does not apply to this study.

## 10.4 Benefits and risks assessment

Since this will be the first clinical trial with the STIL anti-tremor orthosis and patients, no facts about risks and advantages are already known. Therefore, this summary lists the most important *possible* advantages and risks of the device.

#### Advantages

No direct therapeutic effects are expected in this study. We expect that the orthosis will attenuate the tremor of the patient. It does not cure the disorder, but suppresses the tremor when the orthosis is mounted. Patients are not allowed to keep the orthosis after the intervention, since it is not the final product and no CE certification is yet obtained. We do not expect that the effects of the device will last after use.

When the orthosis is on the market and can be used by patients, major advantages for patients with forearm tremor are expected:

- Tremor reduction will have a big impact on the patient's activities of daily life and their social life. Activities they were avoiding or no longer capable of because of the tremor, will be possible again with the orthosis. This will make life a lot easier and comfortable.
- Patients suffering from side-effects of tremor medication, might be able to reduce the amount of medicines taken or potentially even able to stop altogether.
- Together, this will increase the quality of life of the patient.

#### Risks

In case the orthosis functions as supposed to, no severe adverse events are expected. The included patients are not a high-risk population, the orthosis only interacts with intact skin of the arm and hand and will be worn for a maximum of 1 hour (plus another hour for the sham device). Besides, precautionary measures are taken to prevent any risks caused by the orthosis in case of malfunctioning (as explained in section 12 and in the IMDD).

The orthosis is designed in such a way that only safe (bio-compatible) materials interact with the skin. Still, there is a possibility that the orthosis is not comfortable, which could possibly cause transient redness, itchiness, muscle pain or tendon irritation.

In case the orthosis does not function properly, the orthosis can be directly be detached by pulling the designated tabs for quick removal. No risks are expected with regards to the tasks and measurements that will be done in this study. The IMU sensors that will be used imply no additional risk.

## **10.5** Compensation for injury

Reinier de Graaf hospital and STIL have a liability insurance which is in accordance with article 7 of the WMO.

Reinier de Graaf hospital also has an insurance which is in accordance with the legal requirements in the Netherlands (Article 7 WMO). This insurance provides cover for damage to research subjects through injury or death caused by the study.

The insurance applies to the damage that becomes apparent during the study or within 4 years after the end of the study.

#### Insured amounts

A1 € 650.000,= as maximum per claim per subject, with a maximum of

A2 € 5.000.000,= per single medical research, with comprehension that in case the institution conducts of have conducted multiple scientific researches, the total insured amount is limited to A3 € 7.500.000,= for damage caused by scientific research per insurance year.

## Exclusions regarding the test subjects

The insurance does **not** cover the following damage:

- damage due to a risk of which the patient has been informed in the written information.
   This does not apply if the risk is more serious than expected or if the risk was very unlikely to happen;
- health damage that would have occurred even if the patient had not participated in the study;
- damage caused by not (fully) following instructions;
- damage to offspring, as a result of a negative effect of the study on the patient or his / her offspring;
- damage caused by an existing treatment method when investigating existing treatment methods.

## 10.6 Incentives

Patients will receive €0.19 per km for round trip traveling expenditures and parking costs, or the price of public transportation. Patients that are excluded after the inclusion session in the hospital are also entitled to the travel reimbursement.

## **11. ADMINISTRATIVE ASPECTS, MONITORING AND PUBLICATION**

## 11.1 Handling and storage of data, documents and devices

*Clinical investigation data* means all data that was obtained during the study, including digital motion data (captured by the Xsens sensors), digital video data (captured by the webcams), digital notes of the investigator and digital questionnaires.

The only physical documents that are stored in this clinical investigation are the informed consents, the questionnaires during the inclusion protocol, and the questionnaires to validate user satisfaction.

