## 7.3.4 Tremor severity assessment using TETRAS

The principal investigator will quantify the tremor severity using the TETRAS scale. The principal investigator is adequately trained to carry out this assessment. To minimize investigator bias, a second opinion from an independent neurologist will be consulted. These movements and postures are derived from the TETRAS scale  and patient will be asked to perform them for 30 seconds:

- **Eating with a spoon:** Using a spoon to bring peas from a bowl on the table to the mouth. This is an adaptation from the TETRAS scale, as it usually does not specify which solids or liquids must be used to assess eating with a spoon.
- **Drinking from a cup:** Bringing a cup (8 cm tall, filled with water to 1 cm from top) from the table to the mouth to drink water.
- **Pouring:** Pouring a water filled plastic cup (8 cm tall, filled with water to 1 cm from top) into another cup (8 cm tall) that is unsupported on the table.
- Forward outstretched posture: Subjects will bring their arms forward, slightly lateral to midline and parallel to the ground. The wrists should also be straight and the fingers abducted so that they do not touch each other (Figure 6).
- Lateral "wing beating" posture: Subjects will abduct their arms parallel to the ground and flex the elbows so that the two hands do not quite touch each other and are at the level of the nose. The fingers are abducted so that they do not touch each other (Figure 6).

Figure 6. Forward outstretched posture

Lateral wing beating posture

- **Finger-nose-test:** Subjects extend only their index finger. They then touch the examiners finger located to the full extent of their reach, which is located at the same height (parallel to the ground) and slightly lateral to the midline. Subject then touch their own nose (or chin if the tremor is severe) and repeat this back and forth.
- Archimedes spiral: Subjects are asked to copy an Archimedes spiral using a ballpoint pen that approximately fills an A6 sheet of paper (Figure 7). The lines of the spiral should be approximately 1.3 cm apart. The pen should be held in such way that no part of the limb touches the table.

*Figure 7.* Archimedes spiral. The patient will be asked to draw a spiral between the lines, connecting the two dots.

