## 11.1.2 General procedure for handling and storing data and documents

Several general procedures are in place for handling and storing data and documents, in which hardware and software are involved.

Hardware

A hospital laptop with encrypted hard drive will be used for running the clinical investigation CRF software and collecting the patient data. The laptop is not connected to the hospital's network, nor the internet. If the laptop is not used, it will be stored in a closed locker. Throughout the clinical investigation, all motion and video data will remain on the laptop, as a backup. After the clinical investigation, the laptop drive will be formatted.

After each testing, data will be transferred from the laptop, on to the hospital network. For his, an encrypted USB drive will be used. Data is copied to the USB drive, then inserted on a PC that is connected to the network. Data will then be copied to a location on the network only accessible to the investigators. Directly after the data transfer, the transferred data is removed from the USB drive

No data can be stored on the anti-tremor orthosis, nor the motion sensors.

Software

A custom software package – the clinical investigation CRF – is developed to simultaneously capture motion and video data, but also to store the notes of the investigator in a log file. The software is only installed on the laptop of the sponsor, that is used solely for, and during, the clinical investigation. The CRF software will store the data on the laptop's encrypted hard drive.

The collected clinical data (excluding the video and motion data) is also stored within the clinical evaluation software environment, Castor EDC (eCRF), governed by the sponsor. No information from the electronic medical record (Dutch: EPD) is needed. Patients will stay pseudonymized using the 3-digit ID number, and all data will be stored using this code. Data will be processed and stored conform the (AVG) procedures and policies of the Reinier de Graaf hospital, such as two factor authentication before being able to logon to the hospital network and data breach procedures.

Documents

Hard copy files (e.g. informed consents and questionnaires) will be stored for 15 years in a closed cabinet.

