After the data analysis is completed, or at maximum two years after the last patient test, all digital data will be anonymised by deleting the translation key. Digital data that cannot be anonymised, such as the video's recordings, will be removed from the secure network drive. Anonymised data will be stored for 15 years.

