#### APPENDIX I - INSTRUCTIONS ON HOW TO EVALUATE TREMOR PER DOF

TETRAS makes use of different rating scales to rate tremor in different tasks. *Figure 8* displays the three different scales used to assess the tasks relevant to STIL. Tasks consist of the forward outstretched posture, lateral "wing beating" posture, finger-to-nose manoeuvre, spiral drawing, pouring, drinking and eating.

Every posture and ADL task will be scored using the *upper limb tremor scale*. Also, all the different DOFs will be assessed using this scale. Instructions can be found on the next pages, distance between movements is absolute. The ADL tasks will also be scored using the *ADL task scale*, to assess the performance of the exercise.

To assess the spiral drawing, the *spiral scale* will be used. In the video footage two spirals are shown, only assess the first bigger spiral. The scores are defined by whole numbers. However, 0.5-point increments may be used it a rating cannot be reconciled to the higher or lower whole number. Use *figure 9* to fill out your scores.

	RATING SCALE		
Score	Upper limb tremor	Spiral	ADL tasks
0	None	Normal	Normal
0.5	-		
1	< 0.5 cm	Slight; barely visible	Slighty abnormal; presen but does not
			interfere
1.5	0.5 - < 1 cm		
2	1 - < 3 cm	Mild; obvious tremor	Mildy abnormal; some difficulty but can
			complete tasks (little spill)
2.5	3 - < 5 cm		
3	5 - < 10 cm	Moderate; parts not	Moderately abnormal; big spill, change of
		recognizable	strategy
3.5	10 - < 20 cm		
4	≥ 20 cm	Severe; figure not recognizable	Severely abnormal. Cannot do it

Figure 8: TETRAS scales

Patient										
Scale	Upper I	imb trem	nor			Spiral ADL tasks				
Item	Streched	Wing	Nose	Pouring	Drinking	Eating	Spiral	Pouring	Drinking	Eating
Overall										
SIER								$\triangleright$	>	$>\!$
EFE								$\triangleright$	$>\!$	$>\!$
FPS								$\triangleright$	>	$>\!$
WFE								$\triangleright$	$>\!$	$>\!$
FFE								$\geq$	$\geq$	$\geq$

Figure 9: Scoreform

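### The pen-and-paper spirals are missing from the list of stored documents and no masked rating of them is planned, so a cheap safeguard for 4 of the 28 TETRAS points is forgone

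*Protocol*

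**What the plan says.** Protocol 7.1.1 makes the spiral one of seven tasks that sum to at most 28 points per condition. Section 7.3.4 describes the task: "Subjects are asked to copy an Archimedes spiral using a ballpoint pen that approximately fills an A6 sheet of paper". The spiral scale in Appendix I grades the drawing; its top anchor, for example, is "Severe; figure not recognizable".

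On rating, 7.3.4 says "The principal investigator will quantify the tremor severity using the TETRAS scale" and adds a second opinion from an independent neurologist. Appendix I tells the rater: "In the video footage two spirals are shown, only assess the first bigger spiral".

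On storage, 11.1 states: "The only physical documents that are stored in this clinical investigation are the informed consents, the questionnaires during the inclusion protocol". The list ends with the satisfaction questionnaires. Section 11.1.2 is looser: "Hard copy files (e.g. informed consents and questionnaires) will be stored for 15 years in a closed cabinet". Under 11.1.3, digital data that cannot be anonymised, the videos among them, "will be removed from the secure network drive" once the analysis is done and no later than two years after the last test.

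**The concern.** Most TETRAS tasks leave nothing behind except footage and a score. The spiral leaves a sheet of paper that does not show whether a device was worn, or which one. In a single-blind trial whose rater knows the condition, that sheet makes a masked score possible at almost no cost. The protocol recognises rater bias as a risk, since it brings in the second neurologist to limit it, but it does not use the sheet for this purpose and does not list it for storage.

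Two things are at stake: a masked rating of one component of a co-primary endpoint, and a lasting source record against which that component can be verified.

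**Working it through.** This point has no figure of its own to reproduce, so it rests mainly on setting the sections side by side.

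1. **Weight.** One task of seven, 4 points of 28: 4/28 = 14.3% of the TETRAS total.

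2. **What the spiral score measures.** Section 4.4 counts 3 x 9 + 4 x 5 = 47 steps, that is, three tasks with half points and four in whole points. In Appendix I only the spiral and ADL scales have anchors at whole numbers alone. The four whole-point tasks therefore fit spiral, pouring, drinking and eating, with the spiral entering on the scale that grades the drawing. Appendix I also permits half points in unclear cases, so this is a fit and not a proof.

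3. **Source of the score, by condition.**
   - Baseline: 7.3.1 has the principal investigator judge severity from the recordings, and section 3 reuses those results as baseline.
   - Sham and orthosis: 7.3.4 names the rater but not the source. Section 11.1.3 treats the study videos as something to consult if the rating looks abnormal.
   - Result: baseline is tied to video, while the source for the two device conditions is unclear. The conditions being compared could be scored from different sources.

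4. **Masking.** Section 7.2 says the investigator knows the variant. In 11.1.3 the file names include the condition. No masking is stated for the second neurologist. The sham resembles the orthosis, so footage alone may not separate those two, but it would show whether any device is worn, and the file label gives the rest.

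5. **What survives.** Section 11.1 lists no spiral sheets, and no section plans a scan. The videos go under 11.1.3, and the laptop holding the back-up is formatted after the investigation (11.1.2). The scores and the anonymised motion data remain. Neither allows the drawing to be graded again.

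6. **Volume.** 25 patients x 3 conditions = 75 sheets. This is a minimum, because inclusion tasks are done on both sides (7.3.1) and baseline may be repeated at a second visit (section 3).

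7. **Possible bias removed (assumption, not in the documents).** Suppose a rater who knows the condition favours the orthosis by *b* points on every task. The total bias is 7*b*; a masked spiral leaves 6*b*. For *b* from 0 to 0.5 the total runs from 0 to 3.5 points, falling to between 0 and 3.0. Whatever *b* is, one seventh is removed.

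8. **Sample size.** With dz = 4/sqrt(25 + 25 - 2 x 0.5 x 25) = 0.8 and two-sided alpha 0.0125, 21 pairs give power 0.810, which matches the protocol. Nothing here changes it.

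**The case against.** Much of the opposing case stands.

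- **A reader might infer that the spiral endpoint is fixed as scored from video.** The protocol does not go that far. Appendix I gives instructions for judging tremor by degree of freedom, and 4.2 calls on it for eligibility in doubtful cases. Under sham and orthosis the investigator may well score from the sheet. The source is unclear, not fixed as video.
- **A reader might infer that the sheets are thrown away.** Nothing orders that. The wording in 11.1.2 is open-ended, and the list in 11.1 also omits the adverse event form and the device accountability log, which suggests loose drafting. What the text supports is that keeping the sheets is not planned.
- **Re-rating is possible for a time.** The videos remain until analysis is complete, within the two-year limit, and their removal affects all seven tasks.
- **The gain is small.** Six of seven tasks stay as they are, and the IMU co-primary does not depend on a rater's judgement.
- **The count of spirals is a weak contradiction.** Figure 7 is not shown in the text available, and Appendix I already says which spiral is scored.

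What does not stand is the argument that this is only preference. Single blinding is declared openly, but a masked score from retained sheets is less open to bias than any rating the protocol describes, and it needs no new rater.

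**Conclusion.** The point holds as a cheap improvement. The spiral sheets are outside the closed list of stored documents, the only spiral scoring instruction refers to video, the source under sham and orthosis is left unclear, and no masked rating is planned. After the videos are removed, no planned source allows the spiral to be re-rated.

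The direct reach is 4 of 28 points (14.3%) of one co-primary endpoint. That the spiral is the only task leaving a product that can be masked is a fair inference from the task descriptions, not something the protocol states. A sheet hides the device but not the size of the tremor, so the rating would be masked, not free of all bias. The documents give no estimate of rater bias, so its size in points cannot be claimed.

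**What to change.** - In 11.1, add the spiral sheets to the stored documents, and state that they are scanned and kept with the other hard copies.
- Label each sheet with a neutral code that does not show the condition, with the key held separately.
- In 7.3.4, state that the spiral scale is scored from the coded sheets, in random order, for all three conditions. The independent neurologist is the better choice of rater, being less likely to recall the session.
- Make 7.3.4 and Appendix I agree on how many spirals are drawn and which one is scored.

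The cost is a few lines of text and the coding, scanning and filing of at least 75 A6 sheets. One drawback is that the spiral would be rated from a different source than the other six tasks. This is acceptable if the source is the same across conditions, since every comparison is within patient.

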## 11.1.1 Patient pseudonymization

Throughout the clinical investigation, involved patients will be pseudonymized; i.e. their name will be coupled to a random 3-digit number. This accounts for all patient that are in any way involved in the investigation:

- Patients that are selected for screening.
- Patients who are invited for the inclusion.
- Patients who are invited for testing.
- Patient that drop out during any of the above-mentioned steps.

The investigator(s) are the only ones who have access to the translation key. It is the responsibility of the principal investigator to safeguard the key throughout – and after – the clinical investigation.

In case needed, the monitoring committee may have access to the non-pseudonymized data as well. All other concerned staff will only have access to the pseudonymized data.

## 11.1.2 General procedure for handling and storing data and documents

Several general procedures are in place for handling and storing data and documents, in which hardware and software are involved.

Hardware

A hospital laptop with encrypted hard drive will be used for running the clinical investigation CRF software and collecting the patient data. The laptop is not connected to the hospital's network, nor the internet. If the laptop is not used, it will be stored in a closed locker. Throughout the clinical investigation, all motion and video data will remain on the laptop, as a backup. After the clinical investigation, the laptop drive will be formatted.

After each testing, data will be transferred from the laptop, on to the hospital network. For his, an encrypted USB drive will be used. Data is copied to the USB drive, then inserted on a PC that is connected to the network. Data will then be copied to a location on the network only accessible to the investigators. Directly after the data transfer, the transferred data is removed from the USB drive

No data can be stored on the anti-tremor orthosis, nor the motion sensors.

Software

A custom software package – the clinical investigation CRF – is developed to simultaneously capture motion and video data, but also to store the notes of the investigator in a log file. The software is only installed on the laptop of the sponsor, that is used solely for, and during, the clinical investigation. The CRF software will store the data on the laptop's encrypted hard drive.

The collected clinical data (excluding the video and motion data) is also stored within the clinical evaluation software environment, Castor EDC (eCRF), governed by the sponsor. No information from the electronic medical record (Dutch: EPD) is needed. Patients will stay pseudonymized using the 3-digit ID number, and all data will be stored using this code. Data will be processed and stored conform the (AVG) procedures and policies of the Reinier de Graaf hospital, such as two factor authentication before being able to logon to the hospital network and data breach procedures.

Documents

Hard copy files (e.g. informed consents and questionnaires) will be stored for 15 years in a closed cabinet.

